## **11. Endpoints**

The primary endpoint is the recurrence of CRA at any follow-up colonoscopy in both groups during the whole trial. The number, size and location of all adenomas are assessed.

The secondary outcomes are the incidence rates of all polypoid lesions (hyperplastic polyps, inflammatory polyps, serrated polyps, etc.), as well as advanced adenoma or CRC at any follow-up colonoscopy in both groups.

All retrieved polypoid lesions should be sent to local pathology laboratory for histologic evaluation. Two experienced pathologists at each center, who are unaware of the treatment assignments, must review the slides for all removed colorectal lesions. Disagreements in the histologic diagnosis are resolved by re-examination by these two pathologists until agreement is reached. We classify the location of a lesion as right

sided (caecum, ascending colon, hepatic flexure, and transverse colon) or left sided (splenic flexure, descending colon, sigmoid colon, and rectum), and define advanced CRA (A-CRA) as an adenoma with a diameter of 10 mm or more, a villous adenoma ( $\geq 25\%$  villous) or an adenoma with high-grade dysplasia.

## **12. Safety Monitoring**

### **12.1 Observation index**

Safety assessments include adverse events, laboratory tests, EKG, vital signs, etc.

### **12.2 Adverse events (AE)**

An adverse event is any unexpected or unfavorable condition related to any medical treatment during the study period, including an inappropriate sign or symptom, an abnormal lab test or a temporary illness related to the use of the drugs.

We record in time the performance, type, time, extent, duration and outcome of the adverse event.

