## **12.4 Criteria for assessing relationship between adverse events and study drugs**

- A. The time of the adverse event is consistent with the time of medication.
- B. The adverse event is consistent with the known adverse reaction to the drug.
- C. The adverse event cannot be explained by concomitant medication or other reasons.
- D. The adverse event disappears after drug withdrawal.
- E. The same adverse reaction occurs when reusing the drug.

According to the above principles, the causal relationship is divided into five levels: definitely relevant, probably relevant, possibly relevant, possibly irrelevant, and definitely irrelevant.

Definitely relevant: meet the A, B, C, D, E criteria.

Probably relevant: meet the A, B, C, D criteria.

Possibly relevant: meet the A, B criteria.

Possibly irrelevant: meet the A criterion.

Definitely irrelevant: all symptoms can be explained by other reasons, and do not meet all above criteria.

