### ***13.2.3 Safety analysis***

Safety Set (SS) for safety analysis includes all the subjects having received at least one dose of treatment.

Adverse events should be listed, and the  $\chi^2$  test or the Fisher's exact test is used for analyzing the incidence between two groups.

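### Section 12.2 makes relation to a treatment part of the adverse event definition, so unrelated non-serious events need not be classed as AEs or compared between arms; separately, section 12.4 cannot grade a previously unknown reaction above possibly irrelevant

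*Combined protocol and SAP*

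**What the plan says.** Section 12.2 defines the event to be collected: "An adverse event is any unexpected or unfavorable condition related to any medical treatment during the study period". Its list of examples ends with a further tie to use of the drugs, and the recording sentence that follows applies to the adverse event so defined.

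Section 12.1 is broader: "Safety assessments include adverse events, laboratory tests, EKG, vital signs, etc". Section 12.3 defines serious events by outcome and states no relatedness condition.

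Section 12.4 sets five criteria: A (timing), B, C, D (resolution on withdrawal) and E (recurrence on re-use). B reads "The adverse event is consistent with the known adverse reaction to the drug" and C reads "The adverse event cannot be explained by concomitant medication or other reasons". The two upper relevant grades list A, B, C, D and E, and A, B, C and D. The lower grades are:

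- The third and last of the relevant grades: "Possibly relevant: meet the A, B criteria"
- The grade for an event with consistent timing alone: "Possibly irrelevant: meet the A criterion"
- The bottom of the scale, for events with another explanation: "Definitely irrelevant: all symptoms can be explained by other reasons, and do not meet all above criteria"

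Section 13.2.3 lists adverse events, and a chi-square or Fisher's exact test "is used for analyzing the incidence between two groups". It names no other between-arm safety test.

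**The concern.** In a blinded, placebo-controlled trial, the comparison of arms is the best evidence on whether an event is caused by the drug. That works when events are counted whatever the assessor thinks of their cause. If relatedness is part of the definition, the count that 13.2.3 compares depends on an individual opinion. The events most easily judged unrelated include those that nobody yet associates with the drug.

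The causality scale has a related weakness. It makes prior knowledge of a reaction a condition for calling any event relevant. A reaction not previously known could then be reported as irrelevant to the study drug despite strong evidence in the individual case.

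**Working it through.** The plan gives no figure on this point and no expected AE rates, so the check is a reading of the rules plus a count of the 12.4 combinations.

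**Step 1: follow an event through the sections.** Take a non-serious intercurrent event, such as an injury or a respiratory infection, judged unrelated to any treatment.

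- Section 12.2: it fails the definition, so it need not be an AE.
- Sections 7.2.1, 7.2.2, 7.2.4 and 15: it may still be recorded as a symptom or sign, a laboratory result, an ECG result or an abnormal finding. None of these sections has a relatedness test.
- Section 13.2.3: the test is on adverse events, so recording under those sections does not by itself bring the event into the comparison.
- Section 12.4: its lowest grade describes events explained by other reasons, but this event need not reach grading.

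The conflict between 12.2 and 12.4 is partial. Section 12.2 asks about any medical treatment, while 12.4 asks about the study drugs. An event due to a concomitant drug or a procedure can therefore satisfy both. However, criterion C names concomitant medication and other reasons separately, so 12.4 appears to expect AEs with explanations that are not drugs.

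**Step 2: enumerate 12.4.** Five criteria, each met or not met, give 2^5 = 32 combinations, of which 16 have A met. Treat the listed criteria as minimums and give each combination the highest grade whose list it satisfies:

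| A met | Definitely relevant | Probably relevant | Possibly relevant | Possibly irrelevant | Total |
|---|---|---|---|---|---|
| with B | 1 | 1 | 6 | 0 | 8 |
| without B | 0 | 0 | 0 | 8 | 8 |

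The 8 without B are A, AC, AD, AE, ACD, ACE, ADE and ACDE. Adding C, D or E never raises the grade. The case that matters is ACDE: consistent timing, no other explanation, resolution on withdrawal and recurrence on re-use. It is graded possibly irrelevant, below an event that meets only A and B.

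**Step 3: try the other reading.** If the lists are exact, only A, AB, ABCD and ABCDE have a grade among the 16, which leaves 16 − 4 = 12 ungraded. Suppose the last line of 12.4 instead means that not all criteria are met and another explanation exists (C not met). Then 6 of those 12 become definitely irrelevant, and 12 − 6 = 6 stay ungraded: AC, ACD, ACE, ACDE, ABC and ABCE. ACDE has no grade under either version. No reading makes it relevant.

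**Step 4: look for consequences of the grade.** Section 12.3 requires SAE reporting whatever the grade. Section 13.2.3 has no causality filter. The grade therefore affects only how causality is reported.

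**The case against.** The strongest reply is that the plan, read as a whole, collects more than 12.2 suggests. Section 15 asks for all observed results and abnormal findings to be verified and recorded, with no test of relatedness or seriousness. Symptoms and signs, laboratory tests and ECG are recorded in their own right. The irrelevant grades in 12.4 imply that events not due to the study drug were expected. This reply stands as far as recording goes. It does not widen the AE definition, and 13.2.3 tests AEs.

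It is also fair to say that the 12.4 point has limited reach, because no action depends on the grade, and that the 32 combinations are not frequencies. The count shows how the rule works, not how often it would misgrade an event.

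A reader might infer more than the documents support:

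- *Unrelated events go unrecorded.* Section 15 and the observation items say otherwise. Only their classification as AEs is in doubt.
- *A causality screen operates before recording.* No such step is described. It is an inference from the definition.
- *Serious events are lost too.* Section 12.3 states no relatedness condition, so the point is limited to non-serious events.
- *The arms are compared with bias.* Participants and follow-up investigators are blinded (section 3.3), so knowledge of the arm should not drive the judgement.
- *Power to detect harm is reduced.* The documents give no AE rates, and even the direction is open. Leaving out pure background events could sharpen the contrast, while leaving out drug-caused events misjudged as unrelated would weaken it.
- *There is no reference list for B.* Pages were removed from the public copy, so this absence cannot be held against the plan.

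**Conclusion.** The point holds as one of classification and causality grading. Under the wording of 12.2, the 13.2.3 comparison need not include non-serious events judged unrelated to any treatment, even when they are in the trial data. This wording should be reconciled with 12.4. Under 12.4, criterion B alone separates relevant from irrelevant once timing is consistent: 8 of 8 combinations with B against 0 of 8 without, with listed criteria read as minimums. A new reaction meeting A, C, D and E is possibly irrelevant at most, or ungraded if the lists are exact.

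The first part assumes that staff apply 12.2 as written. If they already class all events as AEs, the defect is in the wording alone. The second part needs no assumption about rates and affects causality reporting only. Neither part touches the primary endpoint. Both are worth correcting because the rules as stated misclassify events and the remedy is cheap.

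**What to change.** - **Section 12.2:** define an AE as any untoward medical occurrence in the study period, whether or not it is considered related to a treatment.
- **Section 12.4:** make B supportive rather than mandatory for the three relevant grades, and state that the listed criteria are minimums.
- **Section 13.2.3:** state that the between-arm comparison covers all AEs so defined.

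The cost is protocol wording, more AE entries at contacts already planned (the monthly calls and 3-monthly visits in section 9), and higher reported AE percentages in both arms. The documents do not state the enrolment status. If enrolment has begun, report which AE definition applied in which period, and classify past events from data already recorded where possible.

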### **12.3 Serious adverse events (SAE)**

Serious adverse events are defined as those events that meet any of the following criteria:

- Requires inpatient hospitalization or prolongation of existing hospitalization;
- Results in persistent or significant disability or incapacity;
- Is immediately life threatening or results in death.

Investigators must inform SFDA, sponsor, relevant contract research organization (CRO), ethic committee, and relevant government department by telephone/fax within 24 hours after being aware of the serious adverse event, and file the event in the report form with detailed documents.

The patient should be followed up until clinical recovery or his/her condition has been stabilized.

## **12.4 Criteria for assessing relationship between adverse events and study drugs**

- A. The time of the adverse event is consistent with the time of medication.
- B. The adverse event is consistent with the known adverse reaction to the drug.
- C. The adverse event cannot be explained by concomitant medication or other reasons.
- D. The adverse event disappears after drug withdrawal.
- E. The same adverse reaction occurs when reusing the drug.

According to the above principles, the causal relationship is divided into five levels: definitely relevant, probably relevant, possibly relevant, possibly irrelevant, and definitely irrelevant.

Definitely relevant: meet the A, B, C, D, E criteria.

Probably relevant: meet the A, B, C, D criteria.

Possibly relevant: meet the A, B criteria.

Possibly irrelevant: meet the A criterion.

Definitely irrelevant: all symptoms can be explained by other reasons, and do not meet all above criteria.

## **13. Statistical Analysis Plan (SAP)**

The statistical analysis plan is made and modified by biostatistician and main investigators according to the study protocol before the data is locked. Statistical analysis is based on the statistical plan.

### **13.1 Sample size**

We estimated 918 individuals for recruitment after calculation on the basis of an expected CRA recurrence rate of 21% (30% reduction) for the intervention group and 30% for the placebo group. This study sample size was decided to provide power of 80% at a statistical significance level of 0.05, allowing a 20% dropout rate.

## 13.2 Statistical analysis

### 13.2.1 Balance analysis

Full Analysis Set (FAS) is used in the balance analysis. This analysis set includes all the subjects to the principle of intention to treat (ITT). The subjects must have received at least one follow-up colonoscopy.

A balance analysis is performed for baseline data to evaluate the comparability of the two groups. The baseline data include the number of patients enrolled, the number of clinically evaluable patients, age, weight, symptoms, signs and laboratory tests. In the balance analysis, quantitative variables are described using the mean, standard deviation (SD), normal distribution W test and  $P$  value, etc. The t test or the Wilcoxon rank sum test (if abnormal distribution) is used for comparison the difference between the test drug group and the control group in the statistical analysis. Categorical variables are described using cases and percentages. The chi-square ( $\chi^2$ ) test, the Mantel-Haenszel  $\chi^2$  test or the Fisher's exact test is used for analyzing categorical data.

### 13.2.2 Efficacy analysis

The trial results are evaluated by FAS and Per Protocol Set (PPS). FAS is mainly used to compare the treatment effect for the primary endpoint, and regarding the statistical results from PPS as supplementary analysis. If the subjects have not completed all the treatment, the last exam result will be treated as last observation carried forward (LOCF). Risk ratios (RR) and 95% confidence intervals (CI) are used as the efficacy indicator, comparing by Mantel-Haenszel  $\chi^2$  test methods between the two groups.

Unconditional logistic regression is conducted to compute the odds ratio to estimate the relation between BBR intervention and recurrence of A-CRA and non A-CRA (NA-CRA). Kaplan-Meier method is conducted to estimate progression-free survival of no recurrence of adenoma with log-rank test to compare the survival curve between BBR and placebo group. Survival Curve is used to illustrate time to recurrence of adenoma and RRs are illustrated by Forest plots. We perform predefined subgroup analyses of the primary outcomes to assess BBR effect in terms of age, gender, smoking status, BMI, family history of CRC, number of adenoma and history of CRA.

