### 6.3 Duration

Until the last enrolled patient reached the 2-years follow-up.

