**Table1. Participant timeline**

|                                    | Study Period |        |                 |    |    |    |    |    |    |    |                           |
|------------------------------------|--------------|--------|-----------------|----|----|----|----|----|----|----|---------------------------|
|                                    | Allocati     | Run-in | Post-allocation |    |    |    |    |    |    |    | Closeout                  |
| Time points                        | 0            | -2wks  | M3              | M6 | M9 | 12 | 15 | 18 | 21 | 24 | M24-M36
Final visit    |
| Enrollment:                 |              |        |                 |    |    |    |    |    |    |    |                           |
| Eligibility screen                 | X            |        |                 |    |    |    |    |    |    |    |                           |
| Informed consent                   | X            |        |                 |    |    |    |    |    |    |    |                           |
| Interventions:              |              |        |                 |    |    |    |    |    |    |    |                           |
| BBR
hydrochloride or
placebo |              |        | ◆               |    |    |    |    |    |    | ◆  | Return
unused
pills |
| Assessments:                |              |        |                 |    |    |    |    |    |    |    |                           |
| Demographics                       | X            |        |                 |    |    |    |    |    |    |    |                           |
| Smoking status                     | X            |        |                 |    |    |    |    |    |    |    |                           |
| Height                             | X            |        |                 |    |    | X  |    |    |    | X  |                           |
| Weight                             | X            |        |                 |    |    | X  |    |    |    | X  |                           |
| Medical history                    | X            |        |                 |    |    |    |    |    |    |    |                           |
| Family history                     | X            |        |                 |    |    |    |    |    |    |    |                           |
| Manifestations                     | X            |        | ◆               |    |    |    |    |    |    | ◆  |                           |

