### **7.2.3 *Colonoscopic examination***

Participants at each center are informed to undergo at least one or two follow-up colonoscopies until the last enrolled patient reached the 2-years follow-up, by a training endoscopist to investigate whether new adenoma will be taken place, using a standard colonoscope.

Bowel preparation includes 1000ml polyethylene glycol electrolyte solution administered the previous evening and 2000ml in the early morning before an intraday examination. If the colonoscopy does not reach the caecum, it cannot be included for further analysis and the patient will be required to undergo colonoscopy by another skilled endoscopist on next occasion. The mean colonoscopy withdrawal time are required to be 6 minutes or more.

According to a multiple-center study based of Chinese population [12], the peak of recurrence of adenomas is almost entirely concentrated in the first year, and the first three years follow-up after polypectomy is of critical importance in China. The similar opinions are recommended in *2011 Consensus on the Prevention of Colorectal Tumors in China* [13].

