## **10. Discontinuation of Trial**

1. The case found to be inconsistent with the inclusion criteria after recruitment.
2. It is difficult to adhere to the treatment for the patient who is in a worse condition after medication. In that case, the investigator can suspend the trial and treat as an invalid case.
3. Serious or intolerable adverse events.
4. Serious violation of the study protocol during the study period.
5. Poor compliance.
6. Lost in contact for various reasons.
7. Withdrawal of the consent form by the participant.
8. Discontinuation of trial asked by the sponsor.
9. Discontinuation of trial suggested by the investigators.

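### The last-exam LOCF rule contradicts a primary endpoint that counts an adenoma at any follow-up colonoscopy

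*Combined protocol and SAP*

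**What the plan says.** Section 11 defines the outcome cumulatively: "The primary endpoint is the recurrence of CRA at any follow-up colonoscopy in both groups during the whole trial". Section 13.2.2 makes the FAS the main population for this endpoint and the risk ratio its measure. Between those two statements it gives the scoring rule for subjects who stop early: "If the subjects have not completed all the treatment, the last exam result will be treated as last observation carried forward (LOCF"). The trigger is incomplete treatment, not a missing exam.

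Four other places determine who is affected:

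- Table 1 marks follow-up colonoscopy at months 12 and 24. Section 7.2.3 asks for "at least one or two follow-up colonoscopies until the last enrolled patient reached the 2-years follow-up".
- Lesions found at follow-up are taken out; under section 11 two pathologists "must review the slides for all removed colorectal lesions".
- Treatment runs, per section 6.3, "Until the last enrolled patient reached the 2-years follow-up".
- Section 13.2.1 admits to the FAS only subjects with at least one follow-up colonoscopy.

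**The concern.** For a non-completer with an adenoma at one exam and a clean later exam, section 11 gives an event and the literal wording of section 13.2.2 gives a non-event. Such a subject is realistic. The adenoma is removed, so a clean second exam is plausible. Recurrence is not among the reasons for discontinuation in section 10, so follow-up can continue after a positive exam. Because treatment lasts until the last enrolee reaches two years, an early enrolee can have both scheduled exams and still stop before treatment ends.

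At stake is the primary event count. Two programmers working from this text could derive different primary outcomes. Under the literal rule, the same subject could also be an event in the planned Kaplan-Meier analysis of time to recurrence and a non-event in the risk ratio. LOCF is hardly needed here in any case: every FAS subject has had at least one follow-up exam, so only someone whose sole exam missed the caecum (excluded by section 7.2.3) has nothing to score.

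**Working it through.** **Reproducing the plan's figure.** Inputs from section 13.1: 30% v 21% recurrence, 80% power, significance level 0.05 (two-sided, section 13.2.4), 20% dropout. With pooled variance under the null and mean rate 0.255:

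n = [1.960·√(2·0.255·0.745) + 0.8416·√(0.30·0.70 + 0.21·0.79)]² / 0.09² = 366.99, so 367 per arm, 734 in total; 734/0.80 = 917.5, so 918.

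This matches the plan. Section 5 enrols 1000, which leaves 500 × 0.80 = 400 per arm. Reference power is 80.0% at 367 per arm and 83.3% at 400.

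**Events lost under the literal rule.** The documents give none of the shares needed, so all three are assumptions:

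- d = share of analysed subjects who are non-completers with two evaluable exams, 2% to 20%
- f = share of recurrences found at the first exam, 50% to 90%
- c = share of those who are clean at the second exam, 50% to 90%

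Share of events lost: L = d·f·c. Each observed rate becomes p·(1 − L). Example with d = 5% and f = c = 0.9: L = 0.05 × 0.81 = 4.05%, and the rates become 0.30 × 0.9595 = 0.288 and 0.21 × 0.9595 = 0.201.

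With equal shares in both arms, each cell runs from f = c = 0.5 to f = c = 0.9:

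| d | Events lost | Placebo events lost, of 120 | Power, 400/arm | Power, 367/arm |
|---|---|---|---|---|
| 2% | 0.5-1.6% | 1-2 | 83.0-82.5% | 79.7-79.1% |
| 5% | 1.3-4.1% | 2-5 | 82.7-81.2% | 79.3-77.8% |
| 10% | 2.5-8.1% | 3-10 | 82.0-79.0% | 78.7-75.4% |
| 20% | 5.0-16.2% | 6-19 | 80.7-74.0% | 77.2-70.4% |

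The factor (1 − L) cancels in the ratio, so the risk ratio stays at 0.21/0.30 = 0.70 throughout.

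**Unequal shares, no true effect** (30% in both arms, 400 per arm). The risk ratio becomes (1 − L_BBR)/(1 − L_placebo). For 5% v 2% and f = c = 0.9 this is 0.9595/0.9838 = 0.975. The last column is the chance of a significant result in the direction of the bias, nominally 2.5%.

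| d, BBR v placebo | RR | RR if reversed | Error in that direction |
|---|---|---|---|
| 5% v 2% | 0.992-0.975 | 1.008-1.025 | 2.9-4.2% |
| 10% v 5% | 0.987-0.958 | 1.013-1.044 | 3.3-5.7% |
| 20% v 10% | 0.974-0.912 | 1.026-1.097 | 4.2-11.9% |

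**The case against.** The strongest reply is that LOCF extends the last known status past the point where data stop; it does not normally replace an observed positive. Section 13 says that the analysis plan follows the protocol, so section 13.2.2 should be read to serve the endpoint in section 11. Applied to ever-recurred status, LOCF overwrites nothing, and the time-to-recurrence analysis fits that reading. This is plausible and may well be what was meant. But the sentence refers to the last exam result, not to cumulative status, and no other section settles the matter.

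The second reply is that few subjects are affected, and this largely stands. A subject must be a non-completer with two evaluable exams, positive earlier and clean last. One follow-up exam can satisfy section 7.2.3, and exits such as "Lost in contact for various reasons" (section 10) make a second exam less likely. The 367 and 400 per arm are already net of section 13.1's "allowing a 20% dropout rate", so d = 20% would come on top of that loss. The low rows of the tables are the more likely ones.

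The third reply is that bias needs an imbalance between arms. No document supports one, and the trial is double-blind. That also stands: the unequal-share figures show what is possible, not what is expected.

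**Conclusion.** The concern holds. As written, the rule can turn a confirmed adenoma into a non-event, contrary to the endpoint definition, and the plan does not say that the earlier positive is kept. This is a conflict of wording in the derivation of the primary outcome; it does not show how the data will be programmed.

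The likely effect is small. At an affected share of 2-5%, power at 400 per arm falls by about 0.3 to 2.1 percentage points (83.3% to 83.0-81.2%) and the risk ratio does not change. Larger losses, down to 74.0% at 400 per arm or 70.4% at 367, need a 20% share with f = c = 0.9. Bias needs unequal shares. All these sizes rest on assumed values of d, f and c; the textual conflict does not. It should be fixed because it touches the primary endpoint and costs almost nothing to remove.

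**What to change.** For the primary endpoint, replace the LOCF sentence in section 13.2.2 with a rule such as: a subject counts as a recurrence if any evaluable follow-up colonoscopy shows a histologically confirmed adenoma, regardless of later exams and of treatment completion. This sentence alone resolves the conflict. Keep the risk ratio as the primary analysis.

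A second sentence is worth adding, although it addresses the related matter of unequal exam timing: in the planned Kaplan-Meier and log-rank analysis, censor recurrence-free subjects at their last clean exam, use that analysis as the sensitivity analysis, and report the number and timing of exams by arm.

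The cost is two sentences and a little programming. The sensitivity analysis may be somewhat less precise; the size of that loss was not computed. The sample size of 918 and the primary test do not change, and section 13 allows the plan to be modified before data lock.

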## **4. Selection of Trial Population**

### **4.1 Inclusion criteria**

1. Individuals aged 18-75 years
2. Individuals who had at least one and no more than 6 histologically confirmed CRAs removed within 6 months before recruitment

3. Individuals who are able to swallow pills
4. Individuals who voluntarily sign the consent form after being fully informed and understanding the purpose and procedure of this study, characters of the disease, effect of medication, methods of related examinations, and potential risk/benefits of the study

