## 7. Observation Items

### 7.1 Demographic characteristic & medical history

Gender, age, height, weight, medical history, recent medication, smoking status, history of CRA, family history of CRC, clinical manifestations before enrollment, recent colonoscopy and biopsy, etc.

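### The primary risk ratio is a valid but crude comparison that leaves collected baseline data unused, and the seven subgroup analyses have no interaction test

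*Combined protocol and SAP*

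**What the plan says.** Section 13.2.2 gives the primary efficacy measure and test: "Risk ratios (RR) and 95% confidence intervals (CI) are used as the efficacy indicator, comparing by Mantel-Haenszel" chi-square methods, mainly in the Full Analysis Set. No stratum, centre term or covariate is named there, and section 3.2 names no stratification factor for the randomisation. Regression is planned only by lesion type: "Unconditional logistic regression is conducted to compute the odds ratio to estimate the relation between BBR intervention and recurrence of A-CRA" and non-advanced adenoma.

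The baseline data exist. Section 7.1 lists "Gender, age, height, weight, medical history, recent medication, smoking status, history of CRA, family history of CRC" among the items recorded, together with the recent colonoscopy. Section 4.1 requires "at least one and no more than 6 histologically confirmed CRAs removed within 6 months before recruitment", so adenoma number is known for every eligible participant. Section 13.2.1 says "A balance analysis is performed for baseline data to evaluate the comparability of the two groups", but not how the result enters the efficacy analysis.

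On subgroups, section 13.2.2 says "We perform predefined subgroup analyses of the primary outcomes to assess BBR effect". Seven factors are then listed: "in terms of age, gender, smoking status, BMI, family history of CRC, number of adenoma and history of CRA". The same section says that "RRs are illustrated by Forest plots". It gives no interaction test, and no cut-point for age, BMI or adenoma number. The only significance rule is the general two-sided 0.05 in section 13.2.4.

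**The concern.** Mantel-Haenszel methods are normally chosen to combine strata. With no stratum named, the method reduces to the single 2x2 table. If age, sex, adenoma history and adenoma number predict recurrence, the crude comparison gives up precision that could be had without any new data. Testing balance without saying what follows from it also leaves room for adjustment prompted by the observed imbalance.

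For the subgroups, the question of interest is whether the effect differs between levels. A forest plot of level-specific risk ratios shows the estimates but does not test that difference. Where a factor has to be divided, an unstated cut-point also makes the description of the analyses as predefined incomplete.

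**Working it through.** **1. The plan's own figure.** Inputs: 30% v 21%, power 80%, 20% dropout (section 13.1); two-sided 0.05 (section 13.2.4). With the mean rate 0.255,

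n per arm = [1.960 × √(2 × 0.255 × 0.745) + 0.842 × √(0.30 × 0.70 + 0.21 × 0.79)]² / 0.09² = [1.960 × 0.6164 + 0.842 × 0.6131]² / 0.0081 = 366.99, so 367.

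Total 734, and 734/0.80 = 917.5, so 918, as stated. The sample size therefore rests on an unadjusted comparison.

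**2. Crude power.** Power = Φ{(0.09 − 1.960 × 0.6164/√n) / (0.6131/√n)}. This is 80.0% at 367 per arm. Section 5 plans 1000; less 20% that is 800 evaluable, or 400 per arm, with power 83.3%.

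**3. Adjusted analysis, simulated.** Each scenario had 20,000 trials, with marginal rates held at 30% v 21% and both analyses run on the same data. Assumed, because the documents do not say: 25% with a high adenoma number, standardised age, 50% male, 30% with adenoma history, no centre term, and the C-statistic of the four covariates together. Changes were computed before rounding.

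| Assumed C | Crude, 800 | Adjusted, 800 | Change, 800 (points) | Change, 734 (points) | Median SE ratio |
|---|---|---|---|---|---|
| 0.50 | 0.836 | 0.833 | -0.4 | -0.4 | 1.002 |
| 0.60 | 0.835 | 0.840 | +0.4 | +0.5 | 0.990 |
| 0.67 | 0.834 | 0.857 | +2.2 | +2.2 | 0.968 |
| 0.73 | 0.829 | 0.881 | +5.1 | +5.2 | 0.931 |

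The paired Monte Carlo error is 0.1 to 0.2 points. A run at C = 0.78 gave +7.5 (800) and +8.2 (734). With no treatment effect, rejection at 800 was 0.048–0.054 crude and 0.048–0.052 adjusted.

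**4. Check by formula.** Multiplying both standard errors in step 2 by the SE ratios gives, at 400 per arm, 83.1%, 84.0%, 85.6% and 88.2% against 83.3%: changes of -0.2, +0.7, +2.3 and +4.9. These agree with the table except for about 0.3 points at the weak end. That gap suggests that part of the 0.4-point loss comes from moving to a Wald test on the log risk ratio. A separate simulation of 6,000 trials at 800, with seven non-prognostic covariates, points the same way: crude 0.8313, adjusted log-odds test 0.8307, standardised risk ratio 0.8280 (paired error about 0.2 points).

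**5. Interaction tests.** Seven independent tests at 0.05 give 1 − 0.95⁷ = 0.302, a 30% chance of at least one false positive; simulated on the same patients it was 28–30%. Power for true risk ratios of 0.5 v 0.9, with placebo risk 30% in both levels and 200 per arm in each level:

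var = 2 × 0.70/60 + 0.85/30 + 0.73/54 = 0.0652, SE = 0.255, ln(0.9/0.5) = 0.588, z = 2.30, power = Φ(2.30 − 1.96) = 63%.

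Simulation gave 64% for this half split, 53–60% for a 30/70 split and 40–51% for a 20/80 split.

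**The case against.** The strongest objection is that an unadjusted risk ratio from a randomised trial needs no repair. Its type I error is correct, it matches the sample size, and section 13.2.2 names the measure, the test and the main analysis set. All of that stands. It makes the first part an available improvement and rules out calling it a defect.

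The power gain rests on an assumed C-statistic. That also stands. At C = 0.60 the gain is under half a point, and +5 is simply the result at C = 0.73. It is neither a forecast nor a ceiling.

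Three stronger readings are tempting on subgroups, and the documents do not support them.

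- A reader might infer that each level will be judged by its own P value. With a uniform risk ratio of 0.70 and a half split, power in each level (200 per arm) is 54.2%, so exactly one level would reach P<0.05 in 2 × 0.542 × 0.458 = 50% of trials. But section 13.2.2 does not say that levels will be read this way. It plans risk ratios on a forest plot, and in simulation the two confidence intervals overlapped in 99% of such discordant cases.
- A reader might infer that all seven factors lack cut-points. Only age, BMI and adenoma number need one; smoking status may need its categories stated. Sex, family history and adenoma history are already categorical.
- A reader might infer that cut-points will be picked after the data are seen. The opening of section 13 lets the biostatistician and main investigators modify the SAP until data lock, so a route to fix them exists. The cut-points are missing detail and not evidence of a data-driven choice.

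**Conclusion.** The point holds as a cheap improvement. The primary comparison is crude as written, valid, and consistent with the design. Adjusting for four baseline variables already in hand changes power at 800 evaluable by about -0.4 to +5 points over assumed C-statistics of 0.50 to 0.73, and by more above that. The loss if the covariates are not prognostic is about 0.4 points, part of which may belong to the change of test and not to adjustment. These sizes depend on the section 13.1 rates, 20% dropout from 1000, and the covariate distributions assumed above.

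The subgroup point is secondary but concrete: without an interaction test the planned analyses cannot show whether the effect differs between levels. Adding the tests has limits, since power is about 40–64% even for risk ratios of 0.5 v 0.9, and about 30% of trials with no true interaction would show at least one false positive over seven tests.

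**What to change.** Before unblinding, amend section 13.2.2:

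- **Primary analysis.** Logistic regression on treatment, baseline adenoma number, age (linear), sex and adenoma history, standardised to a marginal risk ratio with a 95% CI (influence-function variance on the log scale). State how missing baseline values are handled. Keep the Mantel-Haenszel risk ratio, described as unstratified, as supportive.
- **Subgroups.** Report one treatment-by-factor interaction P value per factor on the forest plot. Label the subgroups exploratory, and state the low interaction power and the roughly 30% chance of at least one false positive.
- **Cut-points.** Use the pre-lock step in section 13 to fix one blinded cut-point each for age, BMI and adenoma number, for example the pooled median for age and BMI, and 1 v 2–6 adenomas. State the smoking categories as well.

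The cost is a changed primary estimator, SAP text, analysis code and a missing-baseline rule. No new data are needed, and about 0.4 points of power are lost if the covariates turn out not to be prognostic.
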